#### **Missing Day Only**

- If the month and year of the incomplete start date are the same as the month and year of the first administration of the study drug, then the day of the first administration of the study drug will be assigned to the missing day.
- If either the year of the incomplete start date is before the year of the date of the first administration of the study drug or if both years are the same but the month of the incomplete start date is before the month of the date of the first administration of the study drug, then the last day of the month will be assigned to the missing day.
- If either the year of the incomplete start date is after the year of the date of the first administration of the study drug or if both years are the same but the month of the incomplete start date is after the month of the date of the first administration of the study drug, then the first day of the month will be assigned to the missing day.

If the stop date is complete and the imputed start date as above is after the stop date, then the start date will be imputed by the stop date.

If the start date is completely missing and the stop date is complete, then the following algorithm will be used to impute the start date:

- If the stop date is after the date of the first administration of the study drug, then the date of the first administration of the study drug will be assigned to the missing start date.
- If the stop date is before the date of the first administration of the study drug, then the stop date will be assigned to the missing start date.

#### **4.2.4 Pharmacokinetic and Anti-drug Antibody Assessments**

Blood samples will be collected to determine the PK profile of nemolizumab and to assess anti-drug antibodies (ADA). The serum concentration of nemolizumab will be assessed at baseline, weeks 1, 2, 4, 8, 12, 16, 18, and in case of early termination or unscheduled visit for safety reasons. ADA will be assessed at baseline, weeks 4, 8, 12, 16 and 18, and in case of early termination or unscheduled visit for safety reason.

Results will be described in the bioanalytical report, which will be included as an appendix in the final clinical study report.

Nemolizumab serum concentrations will be determined using validated ELISA method by a sponsor representative. A bioanalytical plan describing the details of the bioanalytical work related to serum samples of nemolizumab assessment will be written before the beginning of the sample analysis.

#### **4.2.5 Pharmacodynamic Assessments**

Blood and skin samples (D-Squames and skin biopsies) will be collected according to schedule of assessments to investigate the effect of nemolizumab on selected biomarkers, including but not limited to microbiome, cytokine, chemokine IL-31, IL31-RA.

The PD analyses will be performed by a Sponsor representative. The results will be described in a PD report, which will be included in the final study report.

#### 4.2.6 Biophysical Assessments

##### 4.2.6.1 Actigraphy

High resolution actigraphy will be used in this study to evaluate scratching events and duration of sleep during the night. Philips will, in accordance with procedures, centrally analyze assessment data for scratching events and sleep parameters obtained from the actigraphy device and submit data to the CRO. Patients will wear two devices, one on each wrist, from D-7 and every day during the first 4 weeks of the study, by following the instructions provided by the CRO.

Sleep assessment evaluation will include but not be limited to the parameter 'sleep efficiency'.

Scratching assessment evaluation will include but not be limited to the 2 ratio 'scratching duration/duration' and 'scratching events/duration'.

##### 4.2.6.2 Whole Body Imaging

This device will be used in equipped sites only and the photographs of the entire body will be taken according to the operational manual provided by the Sponsor at least at baseline and Week 12 (Day 85) and if it is possible at Week 4 (Day 29), Week 8 (Day 57), and Week 18 (Day 126). It is for illustration and as exploratory evaluation of the lesions improvement.

## 5 STATISTICAL METHODS

### 5.1 Data Quality Assurance

All tables, figures and data listings (TLFs) to be included in the report will be independently checked for consistency, integrity and in accordance with standard PAREXEL procedures.

### 5.2 General Presentation Considerations

Unless otherwise stated, descriptive summaries will be presented by treatment group. In all tables the treatment groups will be presented in the order of Placebo, Nemolizumab.

Continuous data will be summarized in terms of the mean, standard deviation (SD), median, minimum, maximum, lower quartile (Q1), upper quartile (Q3), and number of observations, unless otherwise stated. Where data are collected over time, both the observed data, change from

baseline and percent change from baseline when appropriate will be summarized at each time point. The minimum and maximum will be reported to the same number of decimal places as the raw data recorded in the database. The mean, median, Q1, and Q3 will be reported to one more decimal place than the raw data recorded in the database. The SD will be reported to 2 more decimal places than the raw data recorded in the database. In general, the maximum number of decimal places reported shall be four for any summary statistic.

Categorical data will be summarized in terms of the number of subjects providing data at the relevant time point (n), frequency counts and percentages. Percentages will be presented to one decimal place. A percentage of 100% will be reported as 100%. Percentages will not be presented for zero counts. Percentages will be calculated using n as the denominator. If sample sizes are small, the data displays will show the percentages, but any textual report will describe frequencies only. Changes from baseline in categorical data will be summarized using shift tables where appropriate.

P-values greater than or equal to 0.001, in general, will be presented to three decimal places. However, if a p-value is only presented to four decimal places (by SAS) it will not be rounded again, but will be presented to four decimal places. P-values less than 0.001 will be presented as “<0.001”, and p-values greater than 0.999 will be presented as “>0.999”.

Confidence intervals (CIs) will be presented to one more decimal place than the raw data.

All report outputs will be produced using SAS® version 9.3 or a later version in a secure and validated environment. The outputs will be provided as individual TLFs in RTF as well as PDF formats and all TLFs in one PDF bundle.

All statistical tests will be two-sided and will be performed at the 5% level of significance, unless otherwise stated.

### **Baseline**

‘Baseline’ is defined as the last available assessment prior to the first planned study drug. The date of the first planned study drug refers to date of the first actual administration of study drug at visit V3/Baseline/Day 1 if exists; otherwise, date of randomization.

For diary data (pruritus NRS, VRS, Sleep disturbance NRS), the baseline values will be derived from data collected during the 7 days prior to the first planned study drug. Baseline score will be the weekly prorated average of non-missing subject diary scores reported during the 7 days. A minimum of 5 daily scores out of the 7 days is required to calculate the weekly prorated average score.

**Analysis Visit**

Study day is relative to date of randomization. Day -1 is the day before randomization, and day 1 is date of randomization.

Assessments at early termination and unscheduled visits will be slotted based on the following visit window.

Period	Analysis Visit	Target day (relative to randomization)	Day ranges
Screening Period	Screening 1	-28	-28 to -8
	Screening 2	-7	-7 to -1
Treatment	Baseline	1	≤1
	Week 1	8	2-11
	Week 2	15	12-22
	Week 4	29	23-43
	Week 8	57	44-71
	Week 12	85	72-99
Follow-up	Week 16	113	100-119
	Week 18	126	>119

The diary reported during study will be classified into analysis visits as follows (i.e., during the 7 days prior to the target day of analysis visit. In this case, the target day of analysis visit is relative to date of the first planned study drug.):

- Day -7 to -1 = Baseline
- Day 1 to 7 = Week 1
- Day 8 to 14 = Week 2
- Day 22 to 28 = Week 4
- Day 50 to 56 = Week 8
- Day 78 to 84 = Week 12
- Day 106 to 112 = Week 16
- Day 120 to 126 = Week 18

These analysis visits will be used in the calculations for all week-based parameters collected on subject's diary (e.g., pruritus NRS, VRS, Sleep disturbance NRS, PAS, DPS, DLQI) Other non-diary data, such as , IGA, vital signs, body weight, clinical laboratory assessments, respiratory assessment/PEF, will be analyzed according to actual scheduled visits.

For efficacy and safety data (except clinical laboratory assessments), where two or more assessments (include both scheduled and unscheduled assessments) are available for the same visit interval, the one closest to the target visit date will be used for the summary and analyses. For clinical laboratory assessments, if repeated measurements are taken for either time point (scheduled visit), then the last measurement will be used for the value for that time point. Unscheduled labs will be included in listings, but not summaries of the data. All post baseline assessments, including repeated or unscheduled visits, will be used for potentially clinically significant value (PCSV) determinations.

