7.1.1 Assessment of pruritus and quality of life by the Subject

7.1.1.1 *Pruritus Numeric Rating Scale (NRS)*

Pruritus NRS ([Appendix 2](#)) is a scale to be used by the subjects to report the intensity of their pruritus (itch) during the last 24 hours all along the study from first screening visit to the follow

up visit. Subjects will receive instructions on how to record their pruritus NRS scores on an electronic device, and will complete the assessment once daily at home in the evening throughout the clinical trial (including the follow-up period).

Subjects will be asked the following questions in their local language:

- For average itch intensity: “On a scale of 0 to 10, with 0 being ‘no itch’ and 10 being ‘worst itch imaginable’, how would you rate your itch overall during the previous 24 hours?”
- For maximum itch intensity: “On a scale of 0 to 10, with 0 being ‘no itch’ and 10 being ‘worst itch imaginable’, how would you rate your itch at the worst moment during the previous 24 hours?”

7.1.1.2 *Verbal rating scale (VRS)*

The VRS ([Appendix 3](#)) consists of a list of adjectives describing different levels of symptom intensity (Phan et al., 2012), to be used by the subjects to report the intensity of their pruritus (itch) over the last 24 hours. Subjects will receive instructions on how to record their pruritus VRS scores on an electronic device, and will complete the assessment once daily in the evening from Screening visit 2 and throughout the clinical trial (including the follow-up period). In the eDiary, patients will mark on a 5-point VRS (Ständer et al. 2013), the response that best describes their pruritus intensity in the last 24 hours.

Subjects will be asked the following questions in their local language:

- For average itch intensity: “On a scale of 0 to 4, with 0 being ‘no itch’ and 4 being ‘very severe itch’, how would you rate your itch overall during the previous 24 hours?”
- For maximum itch intensity: “On a scale of 0 to 4, with 0 being ‘no itch’ and 4 being ‘very severe itch’, how would you rate your worst itch during the previous 24 hours?”

7.1.1.3 *Sleep disturbance Numeric Rating Scale (NRS)*

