20. Instruct the subject on how to use the electronic device to evaluate DPS 24, 48, and 72 hours after study drug administration, and remind subject about the daily evaluation of pruritus NRS, VRS and sleep disturbance NRS.
21. Complete the Subject Enrollment Log.
22. Schedule the next visit V4 Day 8.

8.1.2.2 *Visit 4 / Day 8 Week 1 (+/-1 day) & Visit 5 / Day 15 Week 2 (+/-2 days)*

The Investigator or designee will:

1. Collect information regarding AE (including review of laboratory values) and concomitant therapies/procedures.
2. Perform vital signs measurements.
3. Conduct respiratory medical assessments, including PEF for subjects with a history of asthma
4. When applicable check biopsy healing (for subjects who have consented).
5. Collect PK blood samples.
6. Check subject's record for pruritus NRS and VRS and sleep disturbance NRS
Remind the subject to evaluate NRS and VRS and sleep disturbance NRS daily by completing their device
7. Check subject's use of watches for Actigraphy
8. Schedule the next visit.

8.1.2.3 *Visit 6 / Day 29 Week 4 (+/-2 days) & Visit 7 / Day 57 Week 8 (+/-2 days)*

The Investigator or designee will:

1. Collect information regarding AE (including review of laboratory values) and concomitant therapies/procedures.
2. Perform physical examination & vital signs measurements (**including weight**).
3. Conduct respiratory medical assessments, including PEF for subjects with a history of asthma.
4. Perform ECG at visit 7/Day 57 only
5. Complete urine pregnancy test for female of childbearing potential only.
6. Complete the evaluation of PAS and IGA.
7. Check subject's record for pruritus NRS and VRS & sleep disturbance NRS
8. Ask subject to complete the DPS & DLQI before injection at Visit 6/Day 29 only
9. Collect the watches for Actigraphy analysis at Visit 6/Day29 only
10. Collect urine for urinalysis at Visit 6/Day29 only.
11. Collect blood sample for hematology and entire blood biochemistry, at Visit 6/Day29 only
12. Collect blood samples for biomarkers at Visit 6/Day29 only.

13. Collect PK blood samples for PK and ADA before drug injection.
14. Perform D-Squames sampling at Visit 6/Day29 only.
15. Take whole body photographs (selected centers only) if possible
16. Perform subcutaneous study drug injection and observe for at least 30 minutes before discharging the subject.
9. Remind the subject to complete the device daily
10. Schedule the next visit

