## 4 INVESTIGATIONAL PLAN

### 4.1 Overall Study Design and Plan

This is a randomized, placebo-controlled, double-blinded, parallel group, multicenter study to evaluate the safety and efficacy of nemolizumab in patients suffering from PN. Approximately 70 adult patients suffering from PN for at least 6 months with severe pruritus defined by the mean of the worst daily intensity of the NRS score  $\geq 7$  over the previous week at baseline will be randomized in the study. Subjects meeting inclusion/exclusion criteria will be randomized in a 1:1 ratio to nemolizumab or placebo. Each subject will receive three subcutaneous injections of 0.5mg/kg of nemolizumab or matching placebo. Injections will be administered every 4 weeks (at baseline, week 4 & week 8).

Subjects' participation in the study will be up to 22 weeks, including an up to 4-week screening period, a 12-week treatment period (last study drug injection at week 8) and a 6-week follow-up period (10 weeks after the last study drug injection corresponding to 5 half-lives of nemolizumab).

Assessments of efficacy, safety, PK, PD, and biophysical will be conducted throughout this clinical trial. Refer to Appendix 1 for the complete schedule of assessments.

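### The SAP's Week 1 diary window includes Day 1, a largely pre-dose entry, which dilutes the Week 1 effect by about 7% to 14%; a smaller overlap at Weeks 4 and 8 merits a sensitivity analysis

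*SAP*

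**What the plan says.** SAP 5.2 (Analysis Visit) sorts diary entries into fixed 7-day blocks placed before each nominal visit day. For these blocks, "the target day of analysis visit is relative to date of the first planned study drug". The blocks that matter here are "Day 1 to 7 = Week 1", "Day 22 to 28 = Week 4" and "Day 50 to 56 = Week 8". Baseline is Days -7 to -1. A weekly mean needs at least 5 entries (SAP 4.2.1.1, 4.2.1.2 and 4.2.1.6).

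Protocol 7.1.1.1 has the pruritus NRS entered at home in the evening and asks "how would you rate your itch at the worst moment during the previous 24 hours". The VRS is also an evening entry with a 24-hour recall. The sleep disturbance NRS is a morning entry about the previous night (Protocol 7.1.1.3, SAP 4.2.1.6).

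SAP 4.1 states: "Injections will be administered every 4 weeks (at baseline, week 4 & week 8". The second and third injections are given at the visits that Protocol 8.1.2.3 heads "Visit 6 / Day 29 Week 4 (+/-2 days) & Visit 7 / Day 57 Week 8 (+/-2 days". Days 27-31 and Days 55-59 are therefore permitted dosing days.

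The visit-window table in the same part of SAP 5.2, used to slot early termination and unscheduled assessments, puts Day 1 in Baseline and starts Week 1 at Day 2.

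**The concern.** On Day 1 the injection is the last procedure of a long visit: Protocol 8.1 puts drug administration after all assessments, and 8.1.2.1 lists ECG, blood samples, D-Squames and any biopsies before it. The diary entry that evening therefore looks back largely on untreated time. Because the item asks for the worst moment, even a minority pre-dose share can set the score. For the sleep NRS there is no doubt, since the Day 1 entry rates the night before the first dose. These entries still make up one seventh of the Week 1 mean.

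Change in NRS and VRS at Week 1 is a tested secondary endpoint (SAP 5.7.3.1), and sleep NRS is tested at Week 1 as well (SAP 5.7.4). An effect there would be reported as smaller than it is.

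At Weeks 4 and 8 the question is reversed. The window ends on a fixed day, but the next injection may come up to two days before the nominal visit day. Some entries in the mean can then follow the next dose. Other Week 4 measures are protected against this: DPS and DLQI are completed before the injection (Protocol 8.1.2.3) and PK is drawn pre-dose (Protocol 7.3.1). The diary mean is not. The only rule in SAP 5.7.1.3 that cuts off efficacy data concerns rescue therapy.

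**Working it through.** **Plan's own figure.** SAP 5.10 assumes a difference of 30, SD 35, two-sided 5% and 90% power, and arrives at 30 per group. A noncentral t two-sample calculation gives power 0.894 at 29 per group and 0.904 at 30, so the figure reproduces. It is not in dispute.

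**How much of the Day 1 recall is pre-dose.** Share = (24 - hours from injection to entry)/24. It exceeds one half when the gap is under 12 hours. The documents give no clock times. Assuming injection between 08:00 and 17:00 and entry between 18:00 and 22:00:
- longest gap, 14 h: (24 - 14)/24 = 42%
- injection 12:00, entry 20:00, gap 8 h: 16/24 = 67%
- shortest gap, 1 h: 23/24 = 96%

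**Dilution of the Week 1 mean.** Let Days 2-7 carry the full effect and Day 1 a fraction f of it. The 7-day mean shows (6 + f)/7 of the effect.
- f = 0: 6/7 = 0.857, a 14% loss
- f = 0.5: 6.5/7 = 0.929, a 7% loss

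**Effect on Week 1 power.** Noncentral t, 35 per arm, SD 35, two-sided 5%, noncentrality = (effect/35) × √(35/2). SD 35 and 30 points are the Week 4 planning values, borrowed for Week 1. The 20-point effect is an assumption.

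| Effect on Days 2-7 | Day 1 excluded | f = 0.5 | f = 0 |
|---|---|---|---|
| 20 points | 20.0; power 65% | 18.6; power 59% | 17.1; power 52% |
| 30 points | 30.0; power 94% | 27.9; power 91% | 25.7; power 86% |

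The comparison holds SD at 35 whether the mean uses 6 or 7 days.

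**Entries after the next dose, Weeks 4 and 8.** Count of window days on or after the injection day:

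| Injection day | Window | Entries | Share of 7 | Share of 5 (minimum count) |
|---|---|---|---|---|
| 27 | 22-28 | 2 | 29% | 40% |
| 28 | 22-28 | 1 | 14% | 20% |
| 29-31 | 22-28 | 0 | 0 | 0 |
| 55 | 50-56 | 2 | 29% | 40% |
| 56 | 50-56 | 1 | 14% | 20% |
| 57-59 | 50-56 | 0 | 0 | 0 |

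The entry made on the injection day is itself partly recall from before that dose. For a Day 27 injection and the clock times above, recall after dose 2 totals 1 + gap/24 = 1.04 to 1.58 day-equivalents, or 15% to 23% of the 7-day mean.

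As an upper bound, suppose both entries carry x extra points in full. A subject dosed on Day 27 then shifts by (2/7)x: 1.4 points at x = 5 and 4.3 at x = 15. If a quarter of subjects were dosed that early (assumed), the average shift is 0.25 × 1.4 = 0.4 to 0.25 × 4.3 = 1.1 points, against a planned difference of 30.

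**The case against.** The strongest reply is that the SAP states one rule, the 7 days before the target day, and applies it consistently. That stands. A reader might infer a contradiction, because the visit table starts Week 1 at Day 2. However, that table slots early termination and unscheduled visits, and diary entries have their own rule. The table shows that the SAP treats Day 1 as baseline elsewhere. It does not make the diary rule an error.

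A reader might also infer that the primary endpoint is materially contaminated by dose 2, or biased because only one arm receives drug. The documents do not support this. The visit window is the same in both arms and the trial is double-blind. With no drug effect, neither issue moves the comparison. The 24-hour recall that makes Day 1 largely pre-dose also makes the Day 27 entry partly pre-dose-2.

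Third, Week 1 carries no special weight in this trial. Protocol 3.2 cites first-week onset from earlier studies but seeks an effect here within the first month. DPS at 24, 48 and 72 hours covers early onset separately. Week 1 is one of several secondary time points, with no planned power and no multiplicity adjustment (SAP 5.7.1.4). This limits the importance of the point. It is not a reason to keep a pre-dose entry in an on-treatment mean.

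Finally, cutting the primary window at the second injection while keeping the 5-entry rule could do harm. A subject dosed on Day 27 would have only Days 22-26, and one missed entry would make the primary value missing and send it to LOCF. That objection succeeds against changing the primary definition.

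**Conclusion.** The Week 1 point holds as a minor weakness in the analysis definition. Including Day 1 dilutes the Week 1 effect by about 7% to 14%. The 14% end, and the power figures of 52% and 86%, are upper bounds on the harm because they assume that Day 1 carries no effect. The power figures also rest on Week 4 planning values and, in one row, an assumed 20-point effect. That the evening recall is mostly pre-dose is probable rather than established, since no clock times are given and the low end of the assumed range is 42%. For the sleep NRS the Day 1 entry is wholly pre-dose by the wording of its question. The error is towards the null, so it can understate an early effect but cannot create one.

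The Week 4 and Week 8 overlap exists in the text but is small: at most two entries, only for subjects dosed one or two days early, and an average shift of 0.4 to 1.1 points under the stated assumptions. It is a matter of interpretation, in that the Week 4 mean is not strictly a one-injection result for those subjects. It does not threaten the validity of the primary test.

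**What to change.** 1. In SAP 5.2, define Week 1 for pruritus NRS, VRS and sleep disturbance NRS as Days 2-7 with at least 5 entries. Days 2-8 would be a poorer choice, because Day 8 already opens the Week 2 window (Days 8-14) and would be counted twice.
2. Keep Days 22-28 as the primary Week 4 definition and Days 50-56 for Week 8. Add a sensitivity analysis that uses the 7 days ending the day before the actual second or third injection: Days 20-26 for a Day 27 injection, Days 48-54 for a Day 55 injection. Say that subjects without that injection keep the fixed window.

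The cost is a few lines of SAP text and one extra set of outputs. Daily entries are already held, and Protocol 7.3.1 already has the time of the last injection recorded. The downside of the first change is that Week 1 would tolerate one missed entry instead of two (5 of 6 rather than 5 of 7), so slightly more Week 1 values may be missing. LOCF cannot fill them, because Week 1 is the first post-baseline window. The documents give no diary completion rate, but the number affected can be counted on blinded data before database lock.

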## 4.2 Efficacy and Safety Variables

### 4.2.1 Efficacy Variables

#### 4.2.1.1 Pruritus Numeric Rating Scale (NRS)

Pruritus NRS is a scale to be used by the subjects to report the intensity of their pruritus (itch) during the last 24 hours all along the study from first screening visit to the follow-up visit. Subjects will receive instructions on how to record their pruritus NRS scores on an electronic device and will complete the assessment once daily at home in the evening throughout the clinical trial (including the follow-up period).

Subjects will be asked the following questions in their local language:

- For average itch intensity: “On a scale of 0 to 10, with 0 being ‘no itch’ and 10 being ‘worst itch imaginable’, how would you rate your itch overall during the previous 24 hours?”
- For maximum (Peak) itch intensity: “On a scale of 0 to 10, with 0 being ‘no itch’ and 10 being ‘worst itch imaginable’, how would you rate your itch at the worst moment during the previous 24 hours?”

Weekly prorated average score will be calculated and used in the analysis. If a subject has less than 5 diary entries in a week, the weekly average scores will be set to missing. Refer to Section 5.2 for classification of diary data into analysis week/visit.

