### 4.2.2 Efficacy endpoints

#### 4.2.2.1 Primary endpoint

Percent change from baseline in NRS to week 4 (weekly average of the peak).

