#### 5.7.1.3 Handling of Missing Data

**Use of rescue therapy:** For the purpose of efficacy analysis, subjects receiving any rescue therapies will be considered as treatment failures. All efficacy data, except Observed Case (OC), will be set to missing after rescue medication is used. In OC analysis, observed data after subject has received rescue treatment will be included.

**Diary data:** If a subject has less than 5 diary entries in a week, the weekly prorated average scores will be set to missing. Otherwise the method of computing weekly score when data are missing will be mean replacement approach. i.e. calculation of the overall weekly score a given week as 7 times average of non-missing average of that week.

The following methods will be used to impute the missing values:

**Continuous endpoints:** To impute the missing values for the primary and secondary endpoints, the following imputation approaches will be carried out to assess the robustness of study conclusions with choice of imputation method.

For sensitivity analyses, continuous endpoints will be analysed using analysis of covariance (ANCOVA) including terms of treatment group, country, presence or absence of background of atopy (the stratification factor for randomization to the treatments) and the corresponding baseline value.

1. **Last Observation Carried Forward (LOCF):** The primary imputation method for any missing data will be the LOCF approach. The last observed post-baseline value will be used to replace missing values for continuous variables. For questionnaire-based variables, LOCF will be applied to missing individual questions first, and the value of the total (or sub-scale) score will be derived based on the imputed individual questions.
2. **Observed Case (OC):** No data will be imputed. The observed values are used in analysis, including assessments post rescue medication.
3. **Multiple imputation (MI) method under assumption missing at random (MAR):**

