Multiple Imputation (MI) using the Missing At Random (MAR) assumption will also be used. The MI procedure of the SAS system will be used to generate five sets of data with missing values imputed from observed data. It is expected that the pattern of missing data will be monotonic, with slight deviations being corrected by the Markov Chain Monte Carlo (MCMC) method of the MI procedure. Linear regression will be employed to model the missing NRS score, with the following covariates included in the imputation model: treatment and non-missing data from earlier timepoints.

- **Analysis phase:** The imputed datasets will be analyzed using the methodology described for percent change from baseline in NRS score.
- **Pooling phase:** The results from the analysis of the multiple imputed datasets will be combined by the MIANALYZE procedure of the SAS system.

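### SAP 5.2 defines no weekly diary average for Days 15 to 21, so a missing primary Week 4 value is imputed without the nearest recorded week

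*SAP*

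**What the plan says.** The primary endpoint is the percent change from baseline to Week 4 in the weekly average of peak pruritus NRS (SAP 4.2.2.1). SAP 4.2.1.1 has subjects record the NRS every evening for the whole trial, follow-up included. The same section sets the validity rule: "If a subject has less than 5 diary entries in a week, the weekly average scores will be set to missing".

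Under Analysis Visit, SAP 5.2 assigns diary days to seven post-baseline weeks: Days 1–7, 8–14, 22–28, 50–56, 78–84, 106–112 and 120–126. The line "Day 8 to 14 = Week 2" is followed directly by "Day 22 to 28 = Week 4". The scope is stated: "These analysis visits will be used in the calculations for all week-based parameters collected on" the subject's diary. SAP 5.7.3.1 lists the same NRS weeks, with no Week 3.

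SAP 5.7.1.3 makes LOCF the primary imputation: "The last observed post-baseline value will be used to replace missing values for continuous variables". The MI model takes as covariates "treatment and non-missing data from earlier timepoints".

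**The concern.** The week that sits next to the primary week is collected and then given no place in the derivation. If weekly averages exist only at the listed visits, the latest value available to replace a missing Week 4 is Week 2, even for a subject whose diary for Days 15–21 is complete. LOCF then carries a value from a week further back than it needs to. If the treatment difference is still growing between Weeks 2 and 4, this pulls the estimate towards the earlier, smaller effect. MI lacks the same week, so comparing MI with LOCF would not reveal the problem.

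**Working it through.** **1. The plan's own sample size.** SAP 5.10 gives a difference of 30, SD 35, two-sided 5% and 90% power. The exact two-sample t-test (noncentral t) has power 0.894 at 29 per group and 0.904 at 30, so 30 per group is reproduced. Power at 35 per group is 0.942. The increase from 30 to 35 implies an allowance of 1 − 30/35 = 14.3%.

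**2. Unassigned diary days.** Setting Days 1–126 against the seven windows leaves Days 15–21 (7), 29–49 (21), 57–77 (21), 85–105 (21) and 113–119 (7). The total is 7 + 21 + 21 + 21 + 7 = 77 of 126 days. Days 15–21 are the only gap before the primary timepoint.

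**3. Who is affected.** Assume daily entries are complete up to the last diary day, and apply the 5-of-7 rule:

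| Last diary day | Week 4 source, SAP windows | Week 4 source, Week 3 added |
|---|---|---|
| 1–4 | none | none |
| 5–11 | Week 1 | Week 1 |
| 12–18 | Week 2 | Week 2 |
| 19–25 | Week 2 | Week 3 |
| 26–28 | Week 4 observed | Week 4 observed |

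Only stops on Days 19–25 change source. A subject who completes Days 15–21 and then makes only 1–4 entries in Days 22–28 is affected in the same way.

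**4. Size for LOCF (illustration).** Let m be the share of subjects missing Week 4 and f the share of the Week 4 effect present in the week carried forward. The expected estimate is 30 × (1 − m + m·f). Assumptions: every missing subject has valid Week 2 and Week 3 averages, m is equal in both groups, SD stays at 35, and there are 35 per group. For example, with m = 0.143 and f = 0.50, 30 × (0.857 + 0.0715) = 27.9. With f = 0.75, 30 × (0.857 + 0.107) = 28.9.

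| m | f at Week 2 / Week 3 | Estimate, Week 2 v Week 3 | Power, Week 2 v Week 3 |
|---|---|---|---|
| 5% | 0.50 / 0.75 | 29.3 v 29.6 | 0.931 v 0.937 |
| 14.3% | 0.50 / 0.75 | 27.9 v 28.9 | 0.907 v 0.926 |
| 14.3% | 0.70 / 0.85 | 28.7 v 29.4 | 0.923 v 0.933 |
| 14.3% | 0.90 / 0.95 | 29.6 v 29.8 | 0.936 v 0.939 |
| 14.3% | 1.00 / 1.00 | 30.0 v 30.0 | 0.942 v 0.942 |
| 20% | 0.50 / 0.75 | 27.0 v 28.5 | 0.889 v 0.919 |

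For scale, the standard error of the difference is 35 × √(2/35) ≈ 8.4.

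**5. If not every missing subject has a valid Week 3.** Suppose last diary days were uniform over Days 5–25 (an assumption). Then 7 of 21, one third, would change source. The shift in the 14.3%, 0.50/0.75 case falls from 30 × 0.143 × 0.25 = 1.07 to 1.07/3 = 0.36.

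**6. Later timepoints.** A subject rescued on Day 54 has four usable Week 8 entries (Days 50–53), so Week 8 is missing. The carried value comes from Days 22–28, ending 26 days before rescue, although Days 43–49 may be complete.

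**The case against.** The SAP does not say outright that LOCF works on weekly averages rather than daily entries. SAP 5.2 also slots early-termination and unscheduled assessments by broad windows (Week 2 = Days 12–22, Week 4 = Days 23–43). The schedule marks NRS at such visits, and Protocol 5.8 asks subjects who leave before Week 4 to attend one. A subject who drops out late might therefore have a more recent value than Days 8–14. This stands as a real ambiguity, but it does not close the gap. The diary has its own classification, the broad windows contain no Week 3 either, and Protocol 8.1.4 describes the NRS step at that visit as a check of the subject's record. If another source is meant, it needs stating, because two programmers could derive different primary values.

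Other points stand in full. MI does not rest on Week 2 alone: it uses all the earlier timepoints it has and lacks only Week 3. The observed-case analysis carries nothing forward. Visit-aligned weeks match the protocol's endpoints, which run to each visit, so there is no reason to change what is tabulated. Protocol 1.4 and 3.2 describe onset usually within the first week, which leans towards the flatter cases, although onset is not a plateau.

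A reader might infer that rescue use feeds this problem in the primary analysis. It does not: SAP 5.5.3.3 allows rescue from Day 29, after the Week 4 diary window closes. Dropout and diary non-completion are the routes. Rescue matters only for the later secondary timepoints, and whether the older carried value then misses a worsening is possible but not shown.

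**Conclusion.** The gap is explicit, and its effect on LOCF and MI is the natural reading of the SAP. It concerns only subjects without a valid Week 4 average. In the cases computed, changing the LOCF source moves the estimate by 0 to 1.5 points and power by at most about 3 percentage points. These figures rest on an assumed time course and assumed missing rates. The documents give no weekly profile in prurigo nodularis, and the 14.3% allowance covers drop-outs and major deviations together, so it is not a stated rate of missing NRS. The cases also give every missing subject a valid Week 3, which favours a larger effect.

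A reader might go further and infer that Week 3 would remove most of the LOCF bias, that MI loses material precision, or that the trial is underpowered. The documents support none of these. The first depends on the unknown time course and stop days. The second depends on week-to-week correlations that are not given, and it was not computed. For the third, the sample size reproduces. The point is an avoidable loss of collected information in the primary imputation, small in likely size and worth correcting because the correction is nearly free.

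**What to change.** In SAP 5.2, add derived weekly averages under the same 5-of-7 rule for Week 3 (Days 15–21) and for the other unassigned weeks (Days 29–49, 57–77, 85–105 and 113–119), marked as imputation sources only. In SAP 5.7.1.3, state that LOCF takes the most recent valid weekly average before the missing one, and that Week 3 is a predictor in the MI model for Week 4. State also whether an NRS value from an early-termination or unscheduled visit can ever serve as a source. If leaving out Week 3 is intended, say so and give the reason.

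The tabulated analysis visits and the endpoint definitions stay as they are. The cost is a few lines of SAP text and a small derivation on data already collected, settled before database lock as SAP 5.11 requires.
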